Clinician recruitment will occur through the directors of the participating agencies. Recruitment and retention strategies are based on our prior community trials in which we recruited 80-95% of eligible practitioners and experienced 5-7% attrition. Each agency director will distribute flyers to clinicians in their employ to describe the project and invite them to participate. Agency leaders also will describe the study at staff meetings. Team members will attend professional development and informational meetings throughout the winter and spring of 2020 to answer clinicians' questions, address their concerns, and garner support. Study training activities will fulfill Pennsylvania's annual training requirements for early intervention clinicians, which is a considerable economic benefit to the clinician and the agency. Each clinician will also receive up to \$150 for completing the Project ImPACT training workshop. There will be a local number and e-mail address for staff to contact with any study-related questions.

COVID-19 changes: Clinicians will be paid \$150 for completing the training. The training is now being delivered across 4- 3.5 hour sessions, instead of 2 full days. Clinicians are not able to work during the training and are not paid by the county for the training time, as it is an external training. The compensation was increased to account for the increased time commitment across extended days for the remote training and subsequent loss of wages.

Families

Children and their families will be recruited and retained through clinicians and service coordinators who interact with families during evaluations and individualized family service planning meetings, with a flyer and brief video describing the study. As clinicians are recruited, they will refer families on their caseloads who have not yet responded. Participating families who successfully complete the measures will receive \$50 at each data collection point. There will be a local number for families to call with any questions related to the study protocol.

Consent Process

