All primary data collection will be conducted based on informed parental or practitioner consent. All signed consent forms will be maintained in the case file along with all identifying information in a locked cabinet that is kept in a secure office. The consent form includes the following elements: Purpose, Selection, Procedures, Risks, Costs and Financial Risks, Alternatives, Benefits, Payments, Confidentiality, and Withdrawal.

Clinicians will be informed about the study via a letter from their agency director. The letter will describe the project and ask them to participate. Agency Directors will also describe the study and answer questions at staff meetings and distribute study flyers. Study team members will also attend professional development and informational meetings to address questions and concerns and garner interest and support. Clinicians who are interested will be able to reach out to the study team directly in order to start study procedures.

All six participating agencies will be randomized into three groups based on their agency size and location. Interested clinicians at each agency will be informed of the randomization group during the consent process and are free to decline participation at any time.

Children and families will be recruited and retained through their clinician who is participating in the study as well as service coordinators at participating agencies who interact with families on a regular basis. Clinicians will refer families on their caseload and provide them with a flyer and brief video describing the study. Families who are interested in participating will reach out to a member of the study team in order to have questions and concerns addressed and see if they are eligible to participate.

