In response to COVID-19 informed consent will be obtained electronically. First, an electronic enrollment packet will be e-mailed to individuals who have expressed interest in survey completion. The enrollment packet will include an electronic, informed consent form via the University of Pennsylvania's Qualtrics portal, and an informational flyer about the survey component of the study. The research team will provide detailed information about the study via phone, and participants will complete a screening eligibility survey. If they meet eligibility criteria as outlined in the research protocol, they will view the informed consent document. The consent document includes a description of the study and expected roles and responsibilities of the provider, risks and benefits to participants, and confidentiality procedures. The consent document will also clearly state that participation in the study is completely voluntary, and participants can drop out of the study without penalty at any time. Consent will be obtained through the Qualtrics electronic survey consent form

Subject Compensation

Participating providers and families will be compensated for time spent completing data collection steps.

Providers

Clinicians in the Treatment as usual group will receive \$25 for completing self report fidelity measures after each video recorded observation of their early intervention session. We will observe 3 sessions per family and enroll up to 3 families per provider. They may receive up to \$225 for completed self-report fidelity after observations (3 observations at \$25 each x 3 families)

Clinicians enrolled in one of the ImPACT groups and attend the 2 day project ImPACT interactive workshop and complete the self-paced, online training course, will be compensated \$ 150 for their time. They will also receive the same compensation schedule as clinicians in the Treatment as Usual group for the self report fidelity measures.

Families

Families will receive \$50 at each data collection point. There will be three data collection points for a total of up to \$150.

Data Sharing

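### Clinicians learn their agency's arm during consent and then refer families with no fixed approach order or log, so recruitment below agency level is exposed to arm-dependent selection in all three comparisons

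*Combined protocol and SAP*

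**What the plan says.** Cluster Randomized Study Design allocates six agencies, in two blocks of three, to usual care, ImPACT at 1 hour/week or ImPACT at 4 hours/week. Sample calls for 3 clinicians per agency and 3 children per clinician.

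On clinicians, Consent Process states: "Interested clinicians at each agency will be informed of the randomization group during the consent process and are free to decline participation at any time". The second clinician inclusion criterion under Sample asks for agreement to training and consultation if selected for an ImPACT arm, and gives no time for that agreement.

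On families, the third clinician criterion makes the clinician responsible for identifying them and obtaining consent-to-contact forms. Consent Process adds: "Clinicians will refer families on their caseload and provide them with a flyer and brief video describing the study". A second route is service coordinators: "as well as service coordinators at participating agencies who interact with families on a regular basis". The nearest thing to a sequencing rule is under Recruitment, Families: "As clinicians are recruited, they will refer families on their caseloads who have not yet responded". After that, "Families who are interested in participating will reach out to a member of the study team", and under the remote consent procedure "participants will complete a screening eligibility survey".

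Statistical Analysis for Aim 1 expects similar clinicians and children across groups because agencies are randomly assigned, and will adjust for between-group differences if any are found.

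**The concern.** Randomising agencies balances, in expectation, the agencies and everyone who could be recruited in them. It does not balance those who are recruited if joining or referral happens after the arm is known and may respond to it. Here the clinician knows the arm when deciding to join, and knows it again when deciding which families to refer. If either decision depends on the arm, the arm comparison mixes the effect of the intervention with the effect of who was enrolled. Without a record of families not approached, nobody could judge afterwards whether this had happened.

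**Working it through.** No figure in the plan bears directly on this point, so the check is mainly a reading of the sequence, with some supporting arithmetic.

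**1. Counts.** 6 × 3 = 18 clinicians; 18 × 3 = 54 children; 54 / 3 = 18 children per arm, from 18 / 3 = 6 clinicians and 6 / 3 = 2 agencies per arm. These agree with the protocol.

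**2. Sequence.** Disclosure comes during clinician consent. Referral by those clinicians comes after they join. The eligibility check applies to families who have already come forward. Consent-to-contact forms and the screening survey therefore record responders only. Service coordinators work at the same agencies, and nothing says they are unaware of the arm.

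**3. Does anything differ by arm that could affect joining or referral?** Inputs come from Setting for all Research Activities, Clinician training, Subject Compensation and the design section.

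| What the clinician is asked or offered | Usual care | ImPACT 1 h/week | ImPACT 4 h/week |
|---|---|---|---|
| Training | none described | 25 h stated; listed remote parts 6 + 4 × 3.5 = 20 h | same |
| Maximum pay | 3 × $25 × 3 = $225 | $225 + $150 = $375 | $375 |
| Consultation | none described | biweekly 1-hour group meetings and a monthly 1-hour field visit with feedback | same |
| Weekly contact for 3 children (assuming one clinician delivers it all) | about 3 × 1 = 3 h of specialized instruction | 3 × 1 = 3 h | 3 × 4 = 12 h |

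Each ImPACT arm differs from usual care in training, pay and consultation. The two ImPACT arms differ from each other in weekly hours. So every pair of arms differs in at least one respect.

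The direction is not clear. The training counts toward annual requirements, "which is a considerable economic benefit to the clinician and the agency", but the COVID-19 text in the same section describes lost wages. The extra $150 is $150 / 20 = $7.50 per listed training hour ($150 / 25 = $6.00 on the stated total), and this leaves out consultation time and weekly hours.

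**4. How sensitive is the look for baseline differences?** The plan gives no threshold. If differences are sought by a two-sided 5% test, the standard error of a difference between two arms, in SD units, is sqrt(2 × DE / n), with DE = 1 + (m − 1) × 0.05, using the ICC from Statistical Power.
- Children, no clustering: sqrt(2/18) = 0.33; a difference must exceed 1.96 × 0.333 = 0.65 SD.
- Children within clinicians, m = 3, DE = 1.10: 0.35, so 0.69 SD.
- Children within agencies, m = 9, DE = 1.40: 0.39, so 0.77 SD.
- Clinician characteristics, 6 per arm, no clustering: sqrt(2/6) = 0.58, so 1.13 SD.

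Modest imbalances, even in measured characteristics, would usually pass unnoticed. Unmeasured ones cannot be adjusted for at all.

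**The case against.** The other side has several fair points.

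- *Existing protection.* Baseline Vineland, BOSCC, EIPSES, WHOQOL-BREF, PICCOLO and parent adherence, sociodemographic and clinician covariates, and service use at screening are all collected. Adjustment is planned, and the group-by-time term removes stable level differences. This stands as a reduction of the problem. What is left is selection on unmeasured predictors of change. Blinded scoring of PICCOLO and adherence protects measurement, not enrolment.
- *Wide referral.* The text on families who have not yet responded can be read as referral of everyone remaining. That reading is possible, but the sentence neither requires every family to be approached nor keeps a record.
- *Past recruitment.* In prior trials "we recruited 80-95% of eligible practitioners and experienced 5-7% attrition", which might suggest there is little room for clinicians to select themselves. But 3 per agency is a target, not the yield of an exhausted pool, so those rates cannot be turned into a pool size.
- *Unseen documents.* A log may exist in operational material. If so, a sentence citing it would settle that part.
- *Practicality.* Colleagues in one agency talk, so delaying disclosure clinician by clinician may conceal little. This stands, and the fix is framed by agency for that reason.
- *Proportion.* This is a pilot. With two agencies per arm, balance at agency level is limited as well. That tempers how much weight the point carries, but it does not make agency randomisation a safeguard for those recruited.

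**Conclusion.** The point holds as one of exposure. The protocol sets out a sequence in which clinicians who know the arm decide whether to join and which families to refer, and it does not fix or record whom they approach. The stated expectation of similarity is not secured for recruited clinicians and children.

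Four stronger readings are tempting and are not supported:
- *That bias has occurred.* The documents show only that the route is open.
- *That the problem lies mainly between ImPACT and usual care.* Weekly hours differ between the two ImPACT arms, so the dose comparison is exposed too.
- *That its size can be bracketed* from staff numbers, caseloads or past recruitment rates. The caseload criterion is a minimum of 5 with no upper limit, and the number of eligible clinicians is not given, so such figures bound nothing. Size and direction cannot be derived.
- *That the protocol contradicts itself.* The criterion worded as agreement if selected sits uneasily with disclosure during consent, but it sets no time. The two passages are in tension and need reconciling.

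The conclusion rests on the recruitment, consent, design and analysis sections as they stand. The thresholds in the working assume a 5% test and an ICC of 0.05.

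**What to change.** 1. At any agency where the arm has not yet been disclosed, obtain consent from all interested clinicians before telling any of them the arm. Reconcile Consent Process with the second clinician inclusion criterion under Sample.
2. Have each clinician list, by code, all potentially eligible children (age, classification and service criteria), before disclosure where still possible, and add later ones as they arise. Approach families in a study-generated random order until 3 enrol, or approach all if 3 or fewer are listed. Check parent willingness and tele-health ability at approach, and keep the existing consent-to-contact step. Record by source the families who arrive through service coordinators or contact the team themselves.
3. Log and report, by arm and source, the clinicians and families listed, approached, declining and enrolled. Qualify the similarity statement in Statistical Analysis for Aim 1.

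Where the arm is already known, apply items 2 and 3 to families not yet enrolled and state the limitation for the rest. Consent Process mentions participants who signed earlier consent forms, so some recruitment may predate this version; how many clinicians already know their arm is not stated.

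Cost: protocol wording, one coded list and one log for each of 18 clinicians, and some staff time. Downsides: slightly slower enrolment against the 30-month age limit, possible clinician withdrawal once the arm is disclosed, and residual selection through the other referral routes, which item 2 records but does not remove.

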Clinician Fidelity will be measured using the Project ImPACT Coaching Fidelity Checklist.¹ Clinicians assigned to the two active treatment groups will self-monitor their coaching fidelity as part of the implementation procedure. We also will observe clinicians monthly to ensure accurate self-monitoring in the active treatment groups and to capture the extent to which clinicians in the treatment as usual group use any elements of ImPACT. Previous research indicates high interrater reliability between self and observer ratings on the coaching fidelity form (99% exact agreement);⁴² thus we anticipate that self-ratings will provide an accurate measure of clinician behavior.

Cluster Randomized Study Design

Six agencies will be blocked into groups of 3 based on agency size and location. Within each group of three, each agency will be randomized to one of three conditions: 1) treatment as usual; 2) ImPACT at a dose of 1 hour/week over 6 months; and 3) ImPACT at 4 hours/week over 6 months.

Statistical Analysis for Aim 1

Outcomes will be analyzed as continuous variables at the child or parent level across time. Initially all outcomes will be described using summary statistics (means, medians, and estimates of variance). The longitudinal nested random effects linear models will be used for each outcome; the models will consist of three levels of random effects to adjust for individual child/parent, agency and clinician variability. For each measure, the analysis dataset will contain one observation with each subject's outcome measure at baseline and follow-up. The dependent variable in each model will be the measure of outcome at each time point. The independent variables will include a categorical variable for time period (baseline, 3 months, or 6 months), group (ImPACT_1hr/wk, ImPACT_4hr/wk or comparison), and their interaction. The magnitude and statistical significance of the beta coefficient for the interaction will provide an intent-to-treat assessment of the extent to which the intervention group improved relative to the comparison

group. Because agencies are randomly assigned, we expect clinicians and children in our intervention and comparison groups to be similar across baseline characteristics; however, if we find between-group differences we will control for them in our regression models.

Aim 2: Examine the cost effectiveness of Project ImPACT at different doses.

Overview

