Data will take the form of demographic questionnaires, questionnaires, direct observations, direct assessments and video recordings. Data will be obtained directly from participants in the proposed research project.

Field Observations: We will collect direct observation ratings of provider's coaching fidelity using the Project ImPACT Coaching Fidelity Checklist. We will also collect direct observations of parent/child interactions that will inform the parent's adherence to treatment using the Project ImPACT Intervention Fidelity Checklist and parent responsiveness using the Parenting Interactions with Children: Checklist of Observations Linked to Outcomes (PICCOLO).

Demographic Questionnaires: We will collect sociodemographic information for each participant including information related to race/ethnicity, socioeconomic status, and education level.

Questionnaires: We will collect questionnaires from parents examining their self-efficacy using the Early Intervention Parenting Self-Efficacy Scale (EIPSES), and on their quality of life using the World Health Organization QOL Assessment-Brief (WHOQOL-BREF). We will measure changes in social communication by administering the *Vineland Adaptive Behavior Scales—3rd Edition* with parents. We'll also ask parents to fill out the Project ImPACT Parent Satisfaction Survey to evaluate how satisfied they were with the program overall.

Assessments: We will use the BOSCC to assess children's social communication and play skills from self-recorded 10-minute parent-child play interactions.

COVID-19 changes: All surveys will be administered electronically using a unique secure Redcap survey link. All sessions will be delivered via tele-intervention, consistent with current practice guidelines in the county. Fidelity observations will be conducted via tele-intervention.

Service Use: We will gather data on service use by interviewing parents regarding the total and type of services their child receives. We will interview parents about service use at screening and update during the 3-month and 6-month timepoints using the Service Utilization Survey that the research team will fill out.

COVID-19 changes: Interviews regarding service use will be conducted via telephone/video calls instead of in-person.

Recruitment and Informed Consent

Recruitment

Clinicians

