Since this study constitutes a clinical trial, although we are not studying experimental drugs, the intervention is experimental with the risks described in the Human Subjects section. Therefore, it is appropriate to have a Data and Safety Monitoring Board (DSMB) to monitor the study with an attendant monitoring plan as outlined below. The role of the DSMB will be to ensure that no unexpected untoward consequences of the intervention occur, and if they do, to implement safeguards to decrease or eliminate future risks. Any adverse events will be provided to the DSMB in real time. These adverse events include, but are not limited to, self-injurious behavior or inappropriate or threatening behavior with parents, or clinicians or research staff. Less serious adverse events related to the intervention will be compiled and summarized for the DSMB at their scheduled meetings. All other severe adverse events will be monitored by the principal investigator, the study coordinator, and the assessment team and will be reported to the DSMB regardless of a priori expectation or investigator assessment of likelihood of the study being the cause of the adverse event. The DSMB also will have the power to request further data from the principal investigator based on any concerns raised in the ongoing investigation. At any time during the study, based on its findings, the DSMB can put the study on either temporary hold or stop the study entirely after notifying the principal investigator and the IRB. In the rare case in which they must do so, the DSMB will generate a formal report to the principal investigator, the sponsor, and the IRB. This report would then be modified for a lay reader, a version for past participants and current participants would be produced, and the letter would be sent to all past and current study participants. The DSMB will first meet at the beginning of the study to review its charge and activities. It will then meet quarterly to review non-serious and serious adverse event rates, as well as preliminary efficacy data. It also will meet on an ad hoc basis if the real-time serious adverse events warrant meeting, in their judgment. The format of the meeting will include a presentation of the summarized data by the Principal Investigator ([name]) and the

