biostatistician ([name]). The absolute rates of adverse events as well as the rate compared between the intervention and control groups will be presented. The Board will be composed of two faculty at Penn who are not associated with this intervention but have familiarity with autism intervention, and a senior staff member from Philadelphia's early intervention program.

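### The rules on which less serious adverse events reach the board conflict, and if the related-only summary supplies the between-group comparison, that comparison is tilted against ImPACT

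*Combined protocol and SAP*

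**What the plan says.** All of the reporting rules stand in the Data and Safety Monitoring Plan.

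- Immediate route: "Any adverse events will be provided to the DSMB in real time". No relatedness condition is attached. Later in the section, the provision for ad hoc meetings describes the real-time stream as one of serious events.
- Scheduled route: "Less serious adverse events related to the intervention will be compiled and summarized for the DSMB at their scheduled meetings".
- Severe events: these are passed on whatever their judged cause. The wording, cut one word short here, is "will be reported to the DSMB regardless of a priori expectation or investigator assessment of likelihood of the study being the cause of the adverse".
- Quarterly meetings: "It will then meet quarterly to review non-serious and serious adverse event rates, as well as preliminary efficacy data". No relatedness condition appears here.
- Meeting format: the principal investigator and the biostatistician present summarised data, and "The absolute rates of adverse events as well as the rate compared between the intervention and control groups will be presented".

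The section also fixes what the intervention means: "although we are not studying experimental drugs, the intervention is experimental with the risks described in the Human Subjects section". That is Project ImPACT. Under Cluster Randomized Study Design, "each agency will be randomized to one of three conditions: 1) treatment as usual", and the other two conditions are ImPACT at two doses.

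**The concern.** A relatedness condition does not go with a comparison between randomised groups. Children in usual care are not assigned ImPACT, so their less serious events will hardly ever be judged related to it, while some events on ImPACT will be. A table built on related events therefore applies a different filter in each arm.

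The plan lifts the causality condition explicitly for severe events and keeps it for the less serious events compiled for meetings. It then plans a group comparison without naming the events that go into it. The board may hold or stop the study on its findings, and Potential Risks to Subjects names a possible iatrogenic effect. From a filtered table, a true difference of zero could be read as harm, and a real excess could be dismissed as a product of the filter.

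**Working it through.** **1. Which events supply the comparison?** The plan gives no direct answer, so the sentences have to be set side by side.

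- For the related-only set: the meeting format is a presentation of summarised data, and the related less serious events are the only ones the plan describes as summarised for scheduled meetings. The sentence on compared rates follows directly. If every event already arrived unfiltered in real time, the related-only sentence would have little purpose, and the section itself later treats the real-time stream as serious events.
- For an unfiltered set: the real-time sentence covers any event, the quarterly review covers non-serious rates without a condition, and the comparison sentence speaks of adverse events, not related ones.

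The wording leans towards the first reading but does not settle it.

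**2. Denominators.** From the Sample section and Statistical Power: 6 agencies x 3 clinicians x 3 children = 54 children, and 54 / 3 = 18 per arm. The two ImPACT arms hold 36 children and usual care holds 18.

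**3. Less serious events under the related-only reading.** The plan states no event rate, so there is no figure to reproduce. Assume the same true rate p per child in every arm, a share q of ImPACT events judged related, and a share of 0 in usual care.

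Expected in the summary: ImPACT 36 x p x q; usual care 18 x p x 0 = 0. True counts: 36 x p and 18 x p.

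| p | q | ImPACT shown | Usual care shown | ImPACT true | Usual care true |
|---|---|---|---|---|---|
| 0.10 | 0.1 / 0.3 / 0.5 | 0.36 / 1.08 / 1.8 | 0 | 3.6 | 1.8 |
| 0.20 | 0.1 / 0.3 / 0.5 | 0.72 / 2.16 / 3.6 | 0 | 7.2 | 3.6 |
| 0.40 | 0.1 / 0.3 / 0.5 | 1.44 / 4.32 / 7.2 | 0 | 14.4 | 7.2 |

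At p = 0.20 the ImPACT rate appears as 0.72 / 36 = 2% up to 3.6 / 36 = 10%, and the usual-care rate as 0%. Both are below the true 20%.

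**4. All events combined.** Let s be the share of events that are severe and so exempt from the filter. The plan does not define its severity terms; severe is taken here as the complement of less serious. Under equal true rates the apparent ratio of ImPACT to usual care is (s + (1 - s) x q) / s.

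| s | q = 0.1 | q = 0.3 | q = 0.5 |
|---|---|---|---|
| 0.1 | 1.9 | 3.7 | 5.5 |
| 0.3 | 1.23 | 1.7 | 2.17 |
| 0.5 | 1.1 | 1.3 | 1.5 |

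For severe events alone the ratio is 1.0.

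**5. Unfiltered reading, or after the fix.** With all events counted in all arms, the filter has no effect and the expected ratio under equal true rates is 1.0.

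**The case against.** The strongest reply is that the plan never says unrelated less serious events are withheld. It sends any event to the board in real time, has the board review non-serious rates without a condition, and lets the board ask for further data. On that reading the filter causes no bias. This stands as far as it goes: a reader might infer that the comparison is biased by construction, and the documents do not support that, because the event set behind it is not defined. What remains is a contradiction on which the validity of the table depends.

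Three other strong readings also go too far.

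- A reader might infer that a usual-care child cannot have a related event. Under Clinician Fidelity the plan monitors usual-care clinicians for use of ImPACT elements, so a few such events are conceivable.
- A reader might infer that the board could neither detect nor rule out harm. Severe events reach it whatever their judged cause, and the behaviours listed as examples follow directly on the real-time sentence.
- A reader might infer a fourfold difference in the chance of observing events between the 1-hour and 4-hour arms. The section on the research setting gives 3.4 hours a week of services on average, of which about 1 hour is replaced and the rest retained. The implied totals are 3.4 hours in usual care, 3.4 - 1 + 1 = 3.4 in the 1-hour arm and 3.4 - 1 + 4 = 6.4 in the 4-hour arm, and 6.4 / 3.4 is about 1.9. More events with more treatment may also be a real effect of dose, so this argument is not relied on.

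It is also fair to say that the trial is small and described as minimal risk, and that no formal stopping rule is tied to this table. That limits the consequences but does not remove the contradiction.

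**Conclusion.** The concern holds in conditional form. The plan contradicts itself on which less serious events reach the board, and it leaves undefined the events behind the group comparison. If the compiled related-only summary is used, which the meeting format suggests, the less serious comparison is tilted against ImPACT under equal true rates and absolute rates are understated.

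The direction follows from the wording. The size does not, because p, q and s are all assumptions. Over the ranges shown, the apparent all-event ratio runs from 1.1 to 5.5 when the truth is 1.0. The near-zero usual-care count also assumes that events there are not judged related to an intervention those children were not assigned. The passages should be corrected before the board sees its first comparative table.

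**What to change.** In the Data and Safety Monitoring Plan:

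1. Replace the related-only rule with one that compiles and summarises all less serious adverse events in all three arms regardless of judged relatedness, and report relatedness as a separate column.
2. Reconcile the real-time and scheduled-summary sentences, so that it is clear which events go by which route.
3. State that the compared rates use this unfiltered set, per child, for each of the three arms.

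The cost is a change of wording and a longer event listing for the board. No treatment rule changes.

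Optionally, the same short set of event questions could be put to every family at an interview that already takes place: "We will interview parents about service use at screening and update during the 3-month and 6-month timepoints using the Service Utilization Survey". The 3- and 6-month interviews are the relevant ones, since screening precedes treatment. This would make event collection more uniform across arms, but the correction above does not depend on it.
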